### **Compliance**

Each subject will receive five risankizumab injections during the OLE study. Treatment compliance (TC) will be summarized based on Safety Analysis Set. The treatment compliance is defined as the number of visits that the subject received injections divided by the number of visits a subject is supposed to receive injections during the treatment period (i.e., from the date of the subject's first injection through the date of the last injection). Subjects with missing data for study drug administration will be excluded from the summary. Specifically, TC will be calculated using the following formula:

TC (%) = (number of visits where injections are received/number of visits where injections are supposed to be received) \* 100

The number of visits where injections are supposed to be received for a subject = Max (Round ([Last Study Drug Dose Date – First Study Drug Dose Date – 1]/84 + 1 + 1\*I(Does the Subject Receive the Optional Week 4 dose)),1), where round (x) rounds x to the nearest integer.

The maximum number of visits where injections are supposed to be received will be limited to 5.

The actual drug and dose delivered to the subject will be listed.

**10.0                   Efficacy Analysis****10.1                   General Considerations**

The table below provides the overview of the efficacy analyses to be performed on different endpoints.

There will be no statistical testing and only descriptive statistics will be provided. These include the number of observations, mean, standard deviation, median, minimum and maximum for continuous variables; and frequencies and percentages for categorical or discrete variables.

**Table 8. Summary of Efficacy Variables and Corresponding Analyses**

Efficacy Variables	Summary Method
Categorical Efficacy Endpoints:	
Secondary Binary Endpoint: ACR20 responses at all measured time points	
 
• Point estimates and 95% CIs of the response rates
 
• Imputation: OC
 

Other Categorical Endpoints: At all measured time points:	
 
• Point estimates and 95% CIs of the response rates
 
• Imputation: OC
 

 
• ACR50
 
• ACR70
 
• Minimal disease activity (MDA)
 
• PASI75 response in subjects with a <math>\geq 3\%</math> baseline PsO BSA
 
• PASI90 response in subjects with a <math>\geq 3\%</math> baseline PsO BSA
 
• PASI100 response in subjects with a <math>\geq 3\%</math> baseline PsO BSA
 
• sPGA clear and almost clear in subjects with a <math>\geq 3</math> baseline PsO BSA
 
• Psoriatic Arthritis Response Criteria (PsARC)
 
• European League Against Rheumatism (EULAR) Response
 
• Presence of dactylitis (yes/no)
 
• No Progression of mTSS
 
	
Continuous Efficacy Endpoints	
Secondary Continuous Endpoint: Change from baseline in Study 1311.5 at Week 24 (Study 1311.5), Week 24 (Study M16-244) and Week 48:	
 
• Point estimates, 95% CIs of mean change from baseline together with SD, Min, Q1, Median, Q3 and Max
 
• Imputation: OC
 

Change from baseline in Study M16-244 at all measured timepoints:	
 
• mTSS
 
• HAQ-DI
 
• SF-36
 

**Table 8.****Summary of Efficacy Variables and Corresponding Analyses  
(Continued)**

Other Continuous Endpoints:	
At all measure time points as compared to baseline in Study M16-244:	

• Point estimates, 95% CIs of mean change from baseline together with SD, Min, Q1, Median, Q3 and Max

• For SF-36, spyderdiagram will be provided

• Imputation: OC



• Change in Tender Joint Count (TJC)

• Change in Swollen Joint Count (SJC)

• Change in Dactylitis Count

• Change in SPARCC Enthesitis Index

• Change in mNAPSI

• Change in PhGA(VAS)

• Change in Patient's Assessments of PsA Pain Intensity(VAS)

• Change in PtGA assessments

• Change in High sensitivity C-Reactive Protein (hsCRP)

• Change in DAS28-hsCRP

• Change in LDI

• Change in LEI

• Change in FACIT-FATIGUE

	
Change in BASDAI in subjects with baseline inflammatory spondylitis, based on investigator judgment, in Study 1311.5.	

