5.3.3 Efficacy Variables

The baseline as defined in Study 1311.5 will be used to derive the efficacy endpoints in this study.

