8.1.5 Efficacy Analysis

The baseline for all efficacy analysis in this study will be the baseline in Study 1311.5.

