8.1.5.1 Efficacy Variable

Please see Section [5.3.3](#) for the list of all efficacy endpoints in this study.

A subject will be considered an ACR20/50/70 responder if compared to the baseline in Study 1311.5.

1. The counts for both SJC (66 joints count) and TJC (68 joints count) have reduced by 20%/50%/70% or more; and
2. At least three of the five remaining ACR core set measures show reduction of 20%/50%/70% or more in:
 - a. Patient's Assessment of PsA Pain Intensity (VAS)
 - b. Patient's Global Assessment of Disease Activity (PtGA)
 - c. Physician's Global Assessment of Disease Activity (PhGA)
 - d. Patient's Assessment of Physical Function by Heath Assessment Questionnaire – Disability Index (HAQ-DI)
 - e. High sensitivity C-reactive protein

The other efficacy endpoints will be defined in details in Statistical Analysis Plan (SAP).

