## 6.0 Analysis Conventions

### 6.1 Definition of Baseline

The last non-missing measure collected on or before the day of the first dose of study drug injection in Study 1311.5 for each randomized subject will be used as the Baseline for summary of demographics, disease characteristics and safety analyses. For efficacy endpoints except modified total Sharp score (mTSS), the baseline is defined as the last non missing pre-treatment observation prior to first dose in Study 1311.5. The Baselines for mTSS are defined as the last non-missing observation prior to Day 13 and closest to Day 1 in Study 1311.5.

For mTSS, data for Week 24 in Study 1311.5 and Week 24 in Study M16-244 are considered in analyses. In the context of visits corresponding to mTSS data collection

they will be referred to as Week 24 (Study 1311.5) and Week 24 (Study M16-244) respectively.

If multiple measurements are recorded on the same day, the worst of the multiple measurements will be used.

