### 10.3 Secondary Efficacy Analyses

The following secondary endpoints will be summarized:

- ACR 20 response at all measured time points in Study M16-244
- Change in mTSS at Week 24 (Study 1311.5), Week 24 (Study M16-244), and Week 48 as compared to baseline in Study 1311.5
- Change in HAQ-DI at all measured time points in Study M16-244 compared to baseline in Study 1311.5
- Change SF-36 at all measured time points in Study M16-244 compared to baseline in Study 1311.5

For the change from baseline in continuous endpoints, the number of observations, mean, standard deviation, median, minimum, Q1, Q3 and maximum will be summarized. Point estimates and 95% CIs of mean change from baseline will be provided.

For the summary of binary endpoints by visit, point estimate and 95% CI will be calculated and presented.

The primary analysis for the above secondary efficacy endpoints will be performed based on the Safety Analysis Set with observed cases.

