### 10.4 Further Efficacy Analyses

Further efficacy endpoints will include, but are not limited to, the following:

- ACR 50 response at all measured time points in Study M16-244
- ACR 70 at all measured time points in Study M16-244
- Change in Tender Joint Count at all measured time points in Study M16-244 as compared to baseline in Study 1311.5
- Change in Swollen Joint Count at all measured time points in Study M16-244 as compared to baseline in Study 1311.5
- Change in HAQ-DI at all measured time points in Study M16-244 as compared to baseline in Study 1311.5

- Change in SF-36 at all measured time points in Study M16-244 as compared to baseline in Study 1311.5
- Change in Dactylitis count at all measured time points in Study M16-244 as compared to baseline in Study 1311.5 in subjects with dactylitis at baseline
- Change in SPARCC Enthesitis Index at all measured time points in Study M16-244 as compared to baseline in Study 1311.5 in subjects with enthesitis based on SPARCC sites at baseline
- Change in mNAPSI at all measured time points in Study M16-244 as compared to baseline in Study 1311.5
- Change in PhGA (VAS) at all measured time points in Study M16-244 as compared to baseline in Study 1311.5
- Change in Patient's Assessment of PsA Pain Intensity (VAS) at all measured time points in Study M16-244 as compared to baseline in Study 1311.5
- Change in PtGA assessments at all measured time points in Study M16-244 as compared to baseline in Study 1311.5
- Change in High sensitivity C-Reactive Protein (hsCRP) at all measured time points in Study M16-244 as compared to baseline in Study 1311.5.
- Minimal disease activity (MDA) at all measured time points in Study M16-244
- Change in DAS28-hsCRP at all measured time points in Study M16-244 as compared to baseline in Study 1311.5
- PsO endpoints assessed at all measured time points in Study M16-244 in subjects with a  $\geq 3\%$  baseline PsO BSA in Study 1311.5:
  - PASI 75 and PASI 90 response
  - Change in sPGA clear and almost clear
- EULAR (European League Against Rheumatism) response at all measured time points in Study M16-244
- Change in PsARC (Psoriatic Arthritis Response Criteria) at all measured time points in Study M16-244 as compared to baseline in Study 1311.5
- Presence of dactylitis (yes/no) at all measured time points in Study M16-244 in subjects with dactylitis at baseline

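### SAP Table 8 measures 14 continuous efficacy endpoints from the M16-244 baseline, while the protocol and the rest of the SAP require the Study 1311.5 baseline

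*SAP*

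**What the plan says.** SAP 10.1 introduces Table 8 as the overview of the efficacy analyses. Its block of other continuous endpoints is headed "At all measure time points as compared to baseline in Study M16-244". Beneath it stand 13 bulleted endpoints and one unbulleted item, BASDAI. In the BASDAI line, Study 1311.5 identifies the spondylitis subgroup, not the reference for the change.

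Elsewhere the reference is Study 1311.5:

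- **Protocol 5.3.3:** "The baseline as defined in Study 1311.5 will be used to derive the efficacy endpoints in this study".
- **Protocol 8.1.5:** "The baseline for all efficacy analysis in this study will be the baseline in Study 1311.5".
- **SAP 6.1**, for all efficacy endpoints except mTSS: "the baseline is defined as the last non missing pre-treatment observation prior to first dose in Study 1311.5". The mTSS has its own baseline, also in Study 1311.5.
- **SAP 10.4**, for example: "Change in Tender Joint Count at all measured time points in Study M16-244 as compared to baseline in Study 1311.5". The other 13 endpoints have the same reference there.

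A second Table 8 row, for HAQ-DI and SF-36, reads "Change from baseline in Study M16-244 at all measured timepoints". SAP 10.3 has, for the first of these, "Change in HAQ-DI at all measured time points in Study M16-244 compared to baseline in Study 1311.5", and treats SF-36 alike.

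**The concern.** A programmer who works from Table 8 would compute different mean changes from one who works from SAP 10.4, and both could say they had followed the SAP. For subjects who enter within 4 days, M16-244 Week 0 is the Study 1311.5 Week 24 assessment (Protocol Appendix C, footnote a), taken after that study's treatment. A change measured from there leaves out whatever was gained or lost during Study 1311.5. Some subjects received placebo in that study (SAP 11.2.1 and 11.3), so the omitted part may differ by prior arm.

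Linked outputs would also separate. Protocol 8.1.5.1 ties ACR response to the earlier study: "A subject will be considered an ACR20/50/70 responder if compared to the baseline in Study 1311.5". Under Table 8, most ACR components would be summarised from a different starting point. EULAR response depends on DAS28 improvement from baseline (SAP 10.7.11), yet the DAS28 change itself would be reported from another baseline.

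**Working it through.** There is no planned figure to reproduce. The check is a count, a comparison of texts and one identity.

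**1. Count under the header.** The bullets are TJC, SJC, dactylitis count, SPARCC, mNAPSI, PhGA, pain, PtGA, hsCRP, DAS28-hsCRP, LDI, LEI and FACIT-Fatigue, which makes 13. Adding BASDAI gives 13 + 1 = 14.

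**2. Match to the other sections.**

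| Source | Endpoints covered | Reference |
|---|---|---|
| SAP Table 8 header | 14 | M16-244 |
| SAP 10.4 | 14 of 14 | Study 1311.5 |
| Protocol 5.3.3.3, with the baseline set in 5.3.3 | 14 of 14 | Study 1311.5 |
| Protocol 8.1.5 | all efficacy analyses | Study 1311.5 |
| SAP 6.1 | all efficacy endpoints (mTSS by its own rule) | Study 1311.5 |

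SAP 6.1 contains no M16-244 efficacy baseline. SAP 14.0 says only that this is the first version, so it declares no departure from the protocol.

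**3. ACR components affected.** Six of the seven stand under the header: TJC, SJC, pain, PtGA, PhGA and hsCRP. The seventh, HAQ-DI, is in the other row. It would make 7 of 7 only if that row is read the same way.

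**4. Size of the difference.** Let B be the value at the 1311.5 baseline, W the value at M16-244 Week 0 and V the value at a later visit. For the same subjects,

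V − B = (V − W) + (W − B).

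Table 8 as written reports V − W and drops W − B, the change over Study 1311.5 and any gap of up to 8 weeks before entry. The documents give no data on W − B.

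**5. Illustration with assumed values.** Take TJC with B = 20 and V = 8 at Week 48. Under SAP 10.4 the change is 8 − 20 = −12, a reduction of 12/20 = 60%, which meets the tender-joint part of ACR50. Under Table 8:

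| Assumed W | V − W |
|---|---|
| 20 | 8 − 20 = −12 |
| 14 | 8 − 14 = −6 |
| 8 | 8 − 8 = 0 |

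In the last row, a subject who meets the tender-joint part of ACR50 contributes no improvement to the TJC table.

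**6. The HAQ-DI and SF-36 row.** In "Change from baseline in Study M16-244 at all measured timepoints" the study name can attach to the baseline or to the time points. The extracted table is also misaligned at this place: mTSS, which belongs with the row above, appears beside HAQ-DI and SF-36. This row is the less certain part.

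**7. A related, conditional point on Week 0.** SAP 6.4 assigns visits by Rx Day, and its Week 0 window is Day 1 only. Under SAP 6.3 there is no Rx Day 0, so a Study 1311.5 Week 24 visit held 1 to 4 days before the first M16-244 dose falls on Rx Day −1 to −4, outside that window. The SAP has no rule that places these carried-over results at Week 0.

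**The case against.** The strongest reply is that the documents already settle the matter. Two protocol sections, SAP 6.1 and every matching line of SAP 10.4 name Study 1311.5. Against them stands one header in an overview table, with no M16-244 baseline defined behind it. The study name has probably moved from the time points to the baseline. Linked endpoints separate only if someone follows the header and ignores everything else. ACR response is itself unaffected, nothing is tested, and the example is assumed.

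Most of this stands. It shows the intent, keeps the consequence modest and makes the correction certain. It does not remove the conflict, because the header can be acted on. SAP 6.4 provides a Week 0 window and calls that visit the baseline visit, and Protocol 5.2.1 and 5.3.1.1 also use the term for M16-244 Week 0. Table 8 names the Study 1311.5 baseline in another row, so the two labels can look like a deliberate contrast.

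Two narrower replies also have force. The HAQ-DI and SF-36 row may only be ambiguous, although wording it like SAP 10.3 does no harm under either reading. On Week 0, Appendix C footnote a states the carry-over, and Protocol 10.1 leaves entry of shared data to separate sponsor instructions. Loss of those results is therefore a risk only under literal date-based windowing and only for Week 0 summaries.

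**Conclusion.** The concern holds. The Table 8 header contradicts the protocol and the SAP's own baseline definition for all 14 endpoints beneath it, including 6 of the 7 ACR components. The size in practice is unknown: it equals the mean change from the 1311.5 baseline to M16-244 Week 0, which the documents do not give, and the TJC figures above are assumed. Because the study is descriptive, no test, multiplicity rule or decision is affected. What is at stake is the correctness and labelling of the change-from-baseline tables and their agreement with the response rates. It should be corrected. Confidence is high for the header, lower for the HAQ-DI and SF-36 row, and the Week 0 window is a conditional side point.

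**What to change.** - **Table 8, other continuous endpoints:** give the header the time-point and baseline wording of SAP 10.4, as in "Change in Tender Joint Count at all measured time points in Study M16-244 as compared to baseline in Study 1311.5".
- **Table 8, HAQ-DI and SF-36 row:** use the wording of SAP 10.3, as in "Change in HAQ-DI at all measured time points in Study M16-244 compared to baseline in Study 1311.5".
- **If a change from entry into the extension is also wanted:** define that baseline in SAP 6.1 and label the analysis as additional.
- **Secondary, SAP 6.4:** add one sentence assigning Study 1311.5 Week 24 results carried over under Appendix C footnote a to Week 0. The alternative is to set the Week 0 lower bound to Rx Day −4 in Tables 1 to 4 and 6, which means editing five tables.

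The main correction costs two wording edits, and the Week 0 clarification one sentence. No additional data are collected. An analysis from extension entry, if wanted, would need its own definition and outputs.

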**For Binary Endpoints:**

Estimates of the response rate and the associated 95% confidence interval will be calculated using the exact method.

**For Continuous Endpoints:**

The number of observations, mean, standard deviation, median, minimum, Q1, Q3 and maximum will be summarized. Point estimates and 95% CIs of mean change from baseline will be provided.

## **10.2 Primary Efficacy Analysis**

There is no primary endpoint for this study.

---

### 10.3 Secondary Efficacy Analyses

The following secondary endpoints will be summarized:

- ACR 20 response at all measured time points in Study M16-244
- Change in mTSS at Week 24 (Study 1311.5), Week 24 (Study M16-244), and Week 48 as compared to baseline in Study 1311.5
- Change in HAQ-DI at all measured time points in Study M16-244 compared to baseline in Study 1311.5
- Change SF-36 at all measured time points in Study M16-244 compared to baseline in Study 1311.5

For the change from baseline in continuous endpoints, the number of observations, mean, standard deviation, median, minimum, Q1, Q3 and maximum will be summarized. Point estimates and 95% CIs of mean change from baseline will be provided.

For the summary of binary endpoints by visit, point estimate and 95% CI will be calculated and presented.

The primary analysis for the above secondary efficacy endpoints will be performed based on the Safety Analysis Set with observed cases.

### 10.4 Further Efficacy Analyses

Further efficacy endpoints will include, but are not limited to, the following:

- ACR 50 response at all measured time points in Study M16-244
- ACR 70 at all measured time points in Study M16-244
- Change in Tender Joint Count at all measured time points in Study M16-244 as compared to baseline in Study 1311.5
- Change in Swollen Joint Count at all measured time points in Study M16-244 as compared to baseline in Study 1311.5
- Change in HAQ-DI at all measured time points in Study M16-244 as compared to baseline in Study 1311.5

- Change in SF-36 at all measured time points in Study M16-244 as compared to baseline in Study 1311.5
- Change in Dactylitis count at all measured time points in Study M16-244 as compared to baseline in Study 1311.5 in subjects with dactylitis at baseline
- Change in SPARCC Enthesitis Index at all measured time points in Study M16-244 as compared to baseline in Study 1311.5 in subjects with enthesitis based on SPARCC sites at baseline
- Change in mNAPSI at all measured time points in Study M16-244 as compared to baseline in Study 1311.5
- Change in PhGA (VAS) at all measured time points in Study M16-244 as compared to baseline in Study 1311.5
- Change in Patient's Assessment of PsA Pain Intensity (VAS) at all measured time points in Study M16-244 as compared to baseline in Study 1311.5
- Change in PtGA assessments at all measured time points in Study M16-244 as compared to baseline in Study 1311.5
- Change in High sensitivity C-Reactive Protein (hsCRP) at all measured time points in Study M16-244 as compared to baseline in Study 1311.5.
- Minimal disease activity (MDA) at all measured time points in Study M16-244
- Change in DAS28-hsCRP at all measured time points in Study M16-244 as compared to baseline in Study 1311.5
- PsO endpoints assessed at all measured time points in Study M16-244 in subjects with a  $\geq 3\%$  baseline PsO BSA in Study 1311.5:
  - PASI 75 and PASI 90 response
  - Change in sPGA clear and almost clear
- EULAR (European League Against Rheumatism) response at all measured time points in Study M16-244
- Change in PsARC (Psoriatic Arthritis Response Criteria) at all measured time points in Study M16-244 as compared to baseline in Study 1311.5
- Presence of dactylitis (yes/no) at all measured time points in Study M16-244 in subjects with dactylitis at baseline

- Change in LDI at all measured time points in Study M16-244 as compared to baseline in Study 1311.5 in subjects with dactylitis at baseline
- Change in LEI at all measured time points in Study M16-244 as compared to baseline in Study 1311.5 in subjects with enthesitis based on LEI sites at baseline
- Change in FACIT-FATIGUE at all measured time points in Study M16-244 as compared to baseline in Study 1311.5
- Change in BASDAI at all measured time points in Study M16-244 (in subjects with baseline inflammatory spondylitis, based on investigator judgment, in Study 1311.5) as compared to baseline in Study 1311.5

Further efficacy endpoints will be summarized descriptively. Continuous endpoints will be summarized with the use of box plots, while proportions will be displayed by histograms as appropriate.

## **10.5 Handling of Multiplicity**

There is no multiplicity adjustment needed.

## **10.6 Efficacy Subgroup Analysis**

A subgroup analyses based on prior randomization and weight will be performed to evaluate the consistency of efficacy in the secondary endpoints.

## **10.7 Efficacy Variables Definitions and Conventions**

### **10.7.1 ACR Criteria**

ACR criteria is a commonly used standard criteria mentioned in the guidance of American College of Rheumatology to evaluate the effectiveness of investigational drugs in PsA clinical trials. It is a composite measurement calculated based on the improvement over a set of core measurements.

ACR20 is defined as at least 20% improvement (compared to baseline values) in tender and swollen joint counts and at least 20% improvement in 3 of the remaining 5 core set measures (patient's assessment of pain [VAS], PtGA, PhGA, HAQ-DI and CRP).

ACR50 and ACR70 are similarly defined with at least 50% and 70% improvement, respectively.

### **Calculation Rules for ACR Criteria**

A subject will be classified as an ACR20 (ACR50, ACR70) responder, if the following conditions are met:

1.  $\geq 20\%$  ( $50\%$ ,  $70\%$ ) improvement from baseline in tender joint count (TJC)\* and
2.  $\geq 20\%$  ( $50\%$ ,  $70\%$ ) improvement from baseline in swollen joint count (SJC)\* and
3.  $\geq 20\%$  ( $50\%$ ,  $70\%$ ) improvement from baseline in at least 3 of the following 5:
  - Patient's assessment of pain
  - Patient's Global Assessment of Disease Activity for Arthritis (PtGA)
  - Physician's Global Assessment of Disease Activity for Arthritis (PhGA)
  - Patient's self-assessment of physical function (i.e., measured by Health Assessment Questionnaire (HAQ-DI score)
  - Acute-phase reactant value CRP

There are seven components to be evaluated to define an ACR response. Missing values for each component can occur due to missing assessment, a missed visit or due to dropout from the study. Depending on the pattern of the missing components, ACR responses may be or may not be determined using observed values only.

To maximize the utilization of observed information at certain visits and to be scientifically robust as possible, the principle to calculate ACR response is to minimize imputation whenever possible. "As Observed" ACR responses will be calculated

first based on a derived visit window instead of the nominal visit identifier collected from the CRF.

To calculate "as observed" ACR responses:

- Identify the observed component xx% improvement indicator (0/1/missing), 1 means achieving  $\geq$  xx% improvement from baseline and 0 means < xx% improvement from baseline (e.g., xx% representing 20%/50%/70%).
- ACRxx = 0 if TJC indicator = 0 OR SJC indicator = 0 OR at least 3 out of 5 components improvement indicators = 0;
- ACRxx = 1 if TJC indicator = 1 AND SJC indicator = 1 AND at least 3 out of 5 components improvement indicators = 1
- For all other cases, "as observed" ACRxx = missing since ACRxx cannot be determined.

The following table illustrates examples for as-observed ACR calculations.

Example	TJC 68	SJC 66	Component 1	Component 2	Component 3	Component 4	Component 5	ACR20- Response?
A	1	1	1	1	1	.	.	Yes
B	1	0	1	1	1	1	1	No
C	.	0	.	.	.	.	.	No
D	1	.	1	1	1	1	1	.
E	1	1	0	0	0	1	1	No
F	.	.	0	0	0	.	.	No
G	1	1	1	1	0	0	.	.

Legend: 1 =  $\geq$  20% improved compared to baseline; 0 = < 20% improved compared to baseline; " ." missing

